6.7 Subject replacement

Subjects who are withdrawn or prematurely discontinue trial product will not be replaced.

6.8 Rationale for trial population

The target population for this trial is insulin naïve subjects with T2DM inadequately controlled on SGLT2i treatment \pm OAD treatment. The following types of anti-diabetic pre-trial therapy are allowed: SGLT2i monotherapy or SGLT2i in combination with metformin ± DPP4i ± pioglitazone for a period of at least 90 days prior to screening (inclusion criteria 7). Since pioglitazone should not be combined with dapagliflozin this is specified in the inclusion criteria. Subjects on DPP4i should discontinue this OAD treatment at randomisation. Thus the randomised subjects will be on either SGLT2i monotherapy or SGLT2i ± metformin ± pioglitazone, this treatment should be unchanged throughout the trial, unless there is a safety concern.

To ensure a homogeneous SGLT2i-treated population, subjects may not be treated with other antidiabetic treatment (e.g., other OADs [such as sulfonylureas], or GLP-1 receptor agonists) within 90 days of screening (exclusion criteria 4 and 5). Stable OAD treatment for at least 90 days prior to enrolment is furthermore chosen to minimize carry over effect of OAD treatment on trial endpoints,

Protocol	CONFIDENTIAL	Date:	20 November 2015	Novo Nordisk
Trial ID: NN9068-4229		Version:	2.0	
UTN: U1111-1168-9343		Status:	Final	
EudraCT No.: 2015-001596-48		Page:	28 of 107	

including weight loss secondary to initiation of SGLT2i treatment, and to ensure a population tolerating SGLT2i treatment.

To ensure the safety of the subjects, subjects that are particularly vulnerable due to various illnesses are excluded from participation.

Eligible subjects are presenting with an HbA_{1c} in the range of 7.0-11.0% (both inclusive), while maintaining antidiabetic treatment with SGLT2i as described above. This HbA_{1c} range is chosen to include a representative T2DM population in need of further intensification without imposing an increased risk of hypoglycaemia for the subject.

BMI limits of \geq 20 kg/m² and < 40 kg/m² are chosen to include as broad a population as possible while excluding under-weight individuals in risk of unsafe weight loss, and excluding morbidly obese individuals who may be extremely insulin resistant.

Protocol Trial ID: NN9068-4229 UTN: U1111-1168-9343

EudraCT No.: 2015-001596-48

CONFIDENTIAL

Date: Version: Status: Page:

20 November 2015 | Novo Nordisk Final 29 of 107

7 **Milestones**

Planned duration of the recruitment period i.e. First Subject First Visit (FSFV) – Last Subject First Visit (LSFV): 42 weeks.

End of trial is defined as Last Subject Last Visit (LSLV).

Recruitment:

Recruitment will be closed as soon as the total number of planned subjects to be randomised is achievable, taking the number of screened subjects and the screening failure rate into account.

The screening and randomisation rate will be followed closely via IWRS in order to estimate when to stop screening. All investigators will be notified immediately when the recruitment period ends, after which no further subjects may be screened and the IWRS will be closed for further screening. All subjects included in the screening period and eligible for randomisation can be randomised.

Trial registration:

Information of the trial will be disclosed at clinicaltrials.gov and novonordisk-trials.com. According to the Novo Nordisk Code of Conduct for Clinical Trial Disclosure 18, it will also be disclosed according to other applicable requirements such as those of the International Committee of Medical Journal Editors (ICMJE)¹⁹, the Food and Drug Administration Amendment Act (FDAAA)²⁰, European Commission Requirements $\frac{21,22}{2}$ and other relevant recommendations or regulations. If a subject requests to be included in the trial via the Novo Nordisk e-mail contact at these web sites. Novo Nordisk may disclose the investigator's contact details to the subject. As a result of increasing requirements for transparency, some countries require public disclosure of investigator names and their affiliations.

Protocol Trial ID: NN9068-4229 UTN: U1111-1168-9343

CONFIDENTIAL

Date: Version: Status: Page:

20 November 2015 | Novo Nordisk 2.0 Final 30 of 107

8 Methods and assessments

8.1 Visit procedures

EudraCT No.: 2015-001596-48

The following sections describe the assessments and procedures as well as how to record the results. Timing of the site visits, telephone contacts, visit windows and the assessments to be performed are specified in the flow chart (see section 2).

Investigator assessments

Review of diaries, patient reported outcomes (PROs), laboratory reports, ECGs, eye examinations, physical examinations must be documented with the investigator's dated signature either on the front page of the document and/or in the subject's medical records. The signed documents must be retained at the trial site as source documentation.

Visit schedule

It is the responsibility of the investigator to ensure that all site visits and phone contacts occur according to the flow chart (section 2). A phone contact may be converted to a site visit, if needed.

Date of visit and corresponding visit windows are always calculated in relation to V2 (randomisation) except for V33 which should take place at least 7 days (+3 days) after last dose of trial product and phone contact 34 which should take place at least 30 days (+3 days) after last dose of trial product.

Diaries

At each site visit the subjects will be provided with a new diary. The diary must be collected at the next site visit, and retained at the site as source data in accordance with section 14. However, after V32 the diary will only be collected at the first FU visit (V33), whereas diary data at the second FU contact (P34) will be collected per phone. Consequently, source data will be the notes written by the investigator in the subject's medical record, and be based on an interview performed by phone at the second FU contact (P34).

The investigator is only allowed to record the following data in the diary:

- Subject ID number
- Site contact details
- Time and date of next visit or phone contact
- Prescribed dose of trial product
- Doses and values from SMPG measurements from previous diary, if required to complete next dose adjustment
- Review signature

Protocol
Trial ID: NN9068-4229
UTN: U1111-1168-9343

Date: 20 November 2015 | Novo Nordisk
Version: 2.0
Status: Final

Page:

31 of 107

The subject must record the following information in the diary:

- Date, time and value of the daily pre-breakfast SMPG measurement(s)
- Date, time and value of the 9-point profile SMPG prior to V2, V18 and V32
- Date, time and dose of trial product each day
- Hypoglycaemic episodes (see section 8.5.2)
- Any medical issues

EudraCT No.: 2015-001596-48

• Any changes to concomitant medication (see section 8.3.5)

If the subject is not able to complete the diary themselves (taking exclusion criterion no. 21 into account) and need assistance from a third party to complete the diary, this must be stated in the subject's medical records.

Based on the values from the SMPG measurements, the investigator/subject will assess whether trial product dose needs adjustment according to the titration guideline (Appendix A).

The diary must be reviewed by the investigator to ensure that AEs, including medical issues and concomitant medication, are reported (see section 8.3.2 and 12). In addition, the investigator must consider whether the reported values from the SMPG measurements must be reported as hypoglycaemic episodes (see section 8.5.2).

The investigator or delegated staff should transcribe the diary data to the eCRF as soon as possible, preferable within 24 hours after each site visit/phone contact. Safety data from the diaries must be handled according to the timelines described in Figure 12–1. If data is obtained via phone and a discrepancy is later detected, the values in the eCRF should be corrected according to the diary.

Review of the diary must be documented either on the document and/or in the subject's medical record. If clarification of entries or discrepancies in the diary is needed, the subject must be questioned and a conclusion made in the subject's medical record. Care must be taken not to bias the subject.

8.1.1 Fasting requirements

The subjects should be fasting when attending some of the visits, see flowchart, section $\underline{2}$. Fasting is defined as at least 8 hours without food and drink intake, except for water and other prescribed medication. Trial product and other glucose lowering agents should be withheld on the day of the visit until blood sampling and body weight (if applicable) have been performed. Any other prescribed medication should be taken as usual. If the subject attends a fasting visit in a non-fasting state the blood sampling and body weight procedures should be re-scheduled within the visit window.

Protocol Trial ID: NN9068-4229 UTN: U1111-1168-9343 EudraCT No.: 2015-001596-48

CONFIDENTIAL

Date: Version: Status: Page:

20 November 2015 | Novo Nordisk 2.0 Final 32 of 107

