8.1.5 Follow-up contacts (FU1 and FU2)

FU1 should be scheduled 7 days (+ 3 days) after last dose of trial product and FU2 should be scheduled 30 days (+ 3 days) after last dose of trial product. At FU1 information on antidiabetic treatment, any AEs and hypoglycaemic episodes occurring since visitV32 must be collected and recorded in the eCRF. At FU2 information on antidiabetic treatment and any AEs occurring since V32 must be collected and recorded in the eCRF.

8.1.6 **Unscheduled visits**

Unscheduled visits can be performed at any time at the discretion of the investigator. An unscheduled visit should be performed if:

- An AE occurs that needs further attention
- Additional laboratory samples are needed due to an AE requiring special forms in the eCRF (see section 8.5.1.1)
- A confirmatory pregnancy test is needed
- A blood re-sampling related to a specific visit (if not possible to schedule the re-sampling within the visit window). Only if initial blood sample for some reason was not able to be analysed
- Confirmatory FPG test for rescue criteria evaluation

For the above an unscheduled visit form must be completed in the eCRF, indicating the reason for the visit.

An unscheduled visit form should not be completed if the subject attends the trial site for a blood resampling within the visit window. Instead a requisition form must be completed with the visit number the re-sampling refers to and the data must be entered to the eCRF for the corresponding visit. Also, additional trial product dispensing or auxiliary supply does not require the use of the unscheduled visit form. Additional dispensing session should be made in the IWRS prior to additional trial product dispensing.

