8.2 Laboratory assessments

The laboratory analyses will be handled by a central laboratory. Descriptions of assay methods, laboratory supplies and procedures for obtaining samples, handling, transportation and storage of biological samples and information regarding who will perform the assessments, will be described in a trial specific laboratory manual, provided by the central laboratory (for central laboratory details, see Attachment I).

Laboratory samples not drawn on the day of the actual visit should preferably be drawn on another day within the visit window, see flow chart (section 2). For some of the samples drawn during the trial the subject must be fasting, see the flow chart (section 2) and fasting requirements in section 8.1.1.

The laboratory provides results to the trial sites in the units preferred by the trial sites while the results that are transferred to the trial database will always be in SI units.

The laboratory equipment may provide analyses not requested in the protocol but produced automatically in connection with the requested analyses according to specifications in the laboratory standard operating procedures. Such data will not be transferred to the trial database, but abnormal values will be reported to the investigator.

Laboratory results will be provided by the central laboratory to the investigator on an ongoing basis. For laboratory results outside the normal range the investigator must specify an evaluation on the laboratory report. The evaluation of the results must follow the categories:

- Normal
- Abnormal
 - Was the result clinically significant? (Yes/No)

The investigator must review all laboratory results for concomitant illnesses and AEs and report these according to this protocol (see section 8.3.2 and section 12). The review of laboratory reports must be documented either on the documents and/or in the subject's medical record. The laboratory report must be signed and dated by the investigator on the day of evaluation and the signed report must be retained at the site as source documentation.

The investigator should ensure that all laboratory samples for the subject are shipped to the laboratory immediately after the samples from V1 and V32 (or V32A for prematurely discontinued subjects) have been collected.

All samples will be destroyed on an ongoing basis after the analysis or at the latest at the completion of the clinical trial report (CTR).

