Date: Version: Status: Page:

20 November 2015 | Novo Nordisk 2.0 Final 70 of 107

treating individual subjects with T2DM. For the confirmatory secondary endpoints de jure estimands addressing efficacy are chosen as secondary estimand too.

Only endpoints derived after 26 weeks will be analysed statistically. The expected percentage of missing data is around 15%. In accordance with guidance $\frac{29}{2}$ endpoints will be assessed at frequent visits and also on subjects who prematurely discontinue treatment. If an assessment has been made both at screening and randomisation, and if not otherwise specified, the value from the randomisation visit will be used as the baseline value. If the value measured at the randomisation visit is missing and the assessment also has been made at screening, then the screening value will be used as the baseline value.

Laboratory values below the lower limit of quantification (LLOQ) will be set to ½LLOQ.

The test strategy is hierarchical testing in order to control the familywise Type I error. Inferences will be based on the primary analyses of the primary estimands. The trial will be powered with respect to the primary objective and endpoint.

Presentation of results from a statistical analysis will include the estimated mean treatment effects using LSMean for absolute values, and change from baseline where applicable. The LSMean is either obtained by Rubin's rule weighing together LSMeans from multiple imputation estimations or obtained directly from estimation of a parameterized statistical model. In addition, estimated mean treatment difference (or ratio) will be presented together with the two-sided 95% confidence interval and corresponding two-sided *p*-value.

In the statistical models explanatory factors will be parameterized as follows:

- Treatment: IDegLira, IGlar
- Pre-trial OAD: SGLT2i ± pioglitazone(pio), SGLT2i + metformin(met) ± pio, SGLT2i + $DPP4i \pm pio$, $SGLT2i + met + DPP4i \pm pio$
- Region: Europe (Finland, Hungary, Russia, Slovakia, Slovenia, Spain, Switzerland), North America (CA, USA), South America (Argentina), Asia (India)
- Visit: Planned visits for actual endpoint according flow-chart

The impact of protocol deviations and outliers may be investigated further in sensitivity analyses if deemed relevant.

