(V32A) from subjects prematurely discontinued from randomised treatment. To estimate this estimand for evaluation of non-inferiority of HbA_{1c}, a pattern mixture model approach³⁵ will be adopted. It mimics an ITT scenario where withdrawn and prematurely discontinued subjects from the investigational treatment (IDegLira) arm not having a week 26 measurement are assumed to be switched to a treatment inferior to comparator (IGlar) or any other treatment received after premature treatment discontinuation. This corresponds to a jump to reference (J2R) principle where a penalty in terms of the NI margin is added to withdrawn or prematurely discontinued subjects in the IDegLira arm. Observe that the J2R principle and use of retrieved (V32A) data in analyses will equalise treatment effects and in turn assay sensitivity in the non-inferiority setting may be jeopardized. The penalty of the non-inferiority margin³⁶ is to remedy this. Multiple copies (1000 copies) of the full dataset will be generated by imputing missing values based on estimated parameters for a subgroup of subjects in the trial. This will be done as follows:

- As a first step, all post-randomisation HbA_{1c} values for prematurely discontinued subjects in the investigational treatment group (IDegLira) not having retrieved (V32A) data are set to missing
- In the second step, intermittent missing values are imputed using a Markov Chain Monte Carlo (MCMC) method, in order to obtain a monotone missing data pattern. This imputation is done for each treatment group separately and 1000 copies of the dataset will be generated. Subjects from either group with retrieved (V32A) data will now have a non-missing data pattern
- In the third step, for each of the 1000 copies of the dataset, an ANOVA model with pre-trial OAD and region as factors, and baseline HbA_{1c} as covariate is fitted to the change in HbA_{1c} from baseline to first planned HbA_{1c} measurement visit after randomisation (V10) based on the control group (IGlar) and subjects with retrieved (V32A) data in the investigational group (IDegLira). The estimated parameters, and their variances, from this model are used to impute missing values at the first planned HbA_{1c} measurement visit after randomisation (V10) for subjects in both treatment groups, based on their pre-trial OAD, region and HbA_{1c} at baseline

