1.1 Rationale for the amendment

This amendment has been prepared in order to:

- 1. Update List of abbreviations
- 2. Update the flowchart:
 - deletion of footnote 7 as not applicable in final eCRF
 - update of flowchart and protocol section 8.17 to specify that subjects who premature discontinue trial product should attend V32A in a fasting state
- 3. Clarify the rescue criteria in section 6.5 in order to make it clear that they apply after baseline visit meaning after initiation of treatment
- 4. Update the wording relating to randomisation visit timeframe in section 8.1.3 in order to add an element of flexibility which may be required to accommodate scenarios where an eligible subject is not able to attend for randomisation on day 14 due to force majeure
- 5. Delete the wording relating to randomisation visit timeframe in section 8.1.4 as this is specified in Section 2 Flowchart
- 6. In section 8.2 add that in case of abnormal haematology analysis test results, part of the sample may be kept for up to 2 years
- 7. In section 8.4.1 Height, deletion of text regarding rounding to nearest cm or inch as not applicable in final eCRF
- 8. In section 8.5.2 insert ">" in front of 3.9 mmol/L. In addition, in the 5th bullet in order to align with the diary, specify that date, time, and dose of last anti-diabetic treatment should not be collected in connection with a hypoglycaemic event between V32 and V33
- 9. In section 8.5.5 update text in order to specify that the ECG should be repeated in case the randomisation takes place more than 14 days after the ECG is obtained. In addition delete whom the ECG should be obtained by
- 10. In section 8.6.1, align with the PRO questionnaire that site staff can fill in the headings on the questionnaire forms and review the questionnaire for empty fields and potential adverse events
- 11. In Summary and section 9.1 specify that SGLT2i and metformin not necessarily "will be" but "can be" reimbursed in accordance with local legislation and Ethics Committee approval
- 12. In section 12.1 update serious adverse event with current protocol template text and definition of Major Adverse Cardiovascular Events (MACE)
- 13. In section 12.2 specify that "fasting body weight" should be measured at V32A

- 14. In section 12.5.1 specify forms to be completed
- 15. Update made to section 13.2 in order to align with other parts of the protocol

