Timing of visit (weeks)	<pre></pre>	0	0.53	1	1.5³	2 2	2.5 ³	3 3.53	£23	7 6 3	∞	9 10 11	12	£1 4 51	16	17 18 19 2	20 21-25	25 26	7 days after last trial 5 product	s 30 days after last trial trial	Every 4 weeks	26
Visit window (days)			#	#	H H	TH	#	±1 ±1	1 #1	#	#3	#3	#3	#3	#3	#3	±3 ±3	£3	+3	+3	#3	#3
nse																						
Hand-out and instruct in diary	×	×		×		×		×	×		×		×		×	^	×	×	×			
Collect and review diary		×		×		×	1	×	X		×		×		×	^	X	X	X			
Hand-out and instruct in BG meter	×																					
Attend visit fasting		×							X		X		X		×	X	>	X				X
Make appointment for eye examination																	×	, ,				
Sign off Casebook																				X^{17}		×
End of trial (subject completion)																				X ₁₇		×

¹⁷ Not applicable for subjects that have prematurely discontinued trial product.

CONFIDENTIAL

Date: Version: Status: Page:

28 November 2016 | Novo Nordisk 1.0 Final 11 of 19

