2.7 Section 8.1.7 Premature discontinuation of trial product

Once the two follow-up contacts after discontinuation of trial product are completed the subject should be contacted by phone every 4 weeks. Information on antidiabetic medication and information on potential major cardiovascular events (MACE) and any SAEs occurring since last contact must be collected and recorded in the eCRF. Phone contacts must be documented in the medical record and in the eCRF. The subject should finally come in for a V32A at week 26 to report MACE, SAEs, total daily insulin dose, use of other antidiabetic medication, and have fasting body weight measured and a blood sample taken to measure HbA_{1c}, see flow chart (section 2).

Protocol Amendment 2 Trial ID: NN9068-4229 UTN:U1111-1168-9343

EudraCT No.: 2015-001596-48

CONFIDENTIAL

Date: Version: Status: Page:

28 November 2016 | Novo Nordisk Final 12 of 19

2.8 **Section 8.2 Laboratory assessments**

All samples will be destroyed on an ongoing basis after the analysis or at the latest at the completion of the clinical trial report (CTR). However in case of abnormal haematology analysis test results, part of the sample may be kept for up to 2 years.

2.9 **Section 8.4.1 Body measurements**

Height is measured without shoes in centimetres (cm) or inches. and rounded to the nearest em or inch.

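### Section 8.1.1 defers the HbA1c sample along with the fasting samples when a subject attends non-fasting, which puts primary-endpoint data, V32A included, at a small and avoidable risk

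*Protocol*

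**What the plan says.** Section 8.1.1 defines fasting and then gives the rule for a subject who has eaten. Such a subject attends "in a non-fasting state the blood sampling and body weight procedures should be re-scheduled within the visit window". It does not distinguish one blood sample from another.

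The flow chart marks V2, V10, V14, V18, V22, V26 and V32 as fasting visits. Apart from V1, these are all the on-treatment schedule's HbA1c visits. Amendment 2 (section 1.1, item 2) adds that "subjects who premature discontinue trial product should attend V32A in a fasting state". Its revised section 8.1.7 has the subject come to V32A to "have fasting body weight measured and a blood sample taken to measure HbA_{1c", so the word fasting qualifies the weight. The flow chart shows no FPG or lipid sample at V32A. Visit windows are ±1 day at V10 and ±3 days at V14 to V32 and at V32A.

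Section 8.2 is more selective than 8.1.1: "For some of the samples drawn during the trial the subject must be fasting". HbA1c is drawn at V1, which is not a fasting visit. That value decides eligibility, and if the randomisation value is missing, "then the screening value will be used as the baseline value" (section 17).

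The unscheduled-visit list in section 8.1.6 allows a re-sample when it cannot be fitted into the window, with the qualifier "Only if initial blood sample for some reason was not able to be analysed". In section 17.3.1, step 1 of the primary analysis states that all post-randomisation HbA1c values of prematurely discontinued IDegLira subjects "not having retrieved (V32A) data are set to missing".

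**The concern.** The deferral protects FPG, lipids and fasting weight. It does nothing for HbA1c, which the protocol itself accepts from a non-fasting subject. A site that follows 8.1.1 literally would let a subject who had eaten breakfast leave without giving the primary-endpoint sample, and would depend on a second attendance within a few days. A subject seen on the last day of the window cannot be re-scheduled inside it at all.

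V32A is the visit where this matters most. The primary estimand covers subjects whether or not they stay on treatment, so a measured week-26 value after discontinuation is the most direct evidence for it. Before Amendment 2 that sample could be taken whatever the subject had eaten. The amendment's change for body weight now defers it as well. If the sample is never obtained, the week-26 value is imputed. In the IDegLira arm the subject's earlier HbA1c values are also discarded before imputation.

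**Working it through.** **1. Does the protocol require fasting for HbA1c?**
- V1: HbA1c drawn, visit not fasting, value used for eligibility and as fallback baseline.
- Section 8.2: fasting applies to some samples only.
- Flow-chart footnotes: fasting is attached to FPG and body weight. Section 8.4.2 describes the lipid profile as fasting.
- V32A in version 2.0: HbA1c drawn, visit not marked as fasting.

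No passage makes fasting a condition for HbA1c. Section 8.1.1 defers it only because it refers to blood sampling as a whole.

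**2. What follows if the subject does not return?**
- IDegLira, discontinued, no V32A value: step 1 removes all post-randomisation HbA1c, and steps 3 to 5 impute from a model fitted to IGlar subjects plus IDegLira subjects with retrieved data. Scheduled HbA1c falls at weeks 4, 8, 12, 16 and 20. A subject stopping at week 6 therefore loses one scheduled on-treatment value and one stopping at week 22 loses five, plus the early end-of-treatment value in each case.
- IGlar, discontinued, no V32A value: week 26 is imputed, and earlier values are kept.
- Completer of either arm with no V32 sample: week 26 is imputed by the same sequential models, and earlier values are kept.
- The 0.3% penalty in step 6 applies to every discontinued IDegLira subject, with or without a V32A value, so it does not change.

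**3. The plan's own figures.** Inputs from section 17.1: margin 0.3%, SD 1.0%, one-sided 2.5%, true difference 0.0%, 15% excluded from the per-protocol set. With a noncentral t distribution, 80% power needs 176 per arm, and 176/0.85 = 207.1, rounded up to 208. Power with n per arm uses df = 2n − 2 and noncentrality (0.3 − D)/(SD × √(2/n)). At n = 208 and D = 0.045% the noncentrality is 0.255/√(2/208) = 2.60 and power is 0.737, as in Table 17–1. The other cells of that table also reproduce. The sample size is not in question.

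**4. Number of subjects exposed.** Section 6.1 gives 416 − 354 = 62 not completing on trial product, about 31 per arm (15% × 208 = 31.2). This is an upper limit for V32A, because subjects who withdraw from the trial never reach it.

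**5. Size.** The documents give no rate of non-fasting attendance without return, so the rates below are assumptions. Lost subjects are treated as contributing nothing, which is a crude approximation. Power is at D = 0.045%, SD 1.0%.

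| Unrecovered share at V32A | Lost per arm | Lost in total | Power | Change (points) |
|---|---|---|---|---|
| 0% | 0 | 0 | 0.7371 | – |
| 2% | 0.62 | 1.25 | 0.7358 | −0.1 |
| 5% | 1.56 | 3.12 | 0.7339 | −0.3 |
| 10% | 3.12 | 6.24 | 0.7307 | −0.6 |
| 20% | 6.24 | 12.48 | 0.7241 | −1.3 |

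The rule also applies at V32. If 1% or 2% of all 416 week-26 samples were lost (4.2 or 8.3 values), power would be 0.733 or 0.729.

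**6. Direction of bias.** With nA and nB values lost in the IDegLira and IGlar arms, and gaps δA and δB between the true and imputed means, the shift in D is (nA × δA − nB × δB)/208. For equal losses and equal gaps it is zero.

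**The case against.** The best case for the plan is that the sample is postponed and not given up. Section 8.2 states re-drawing within the window only as a preference, so a later draw is not barred. Section 8.1.6 opens by allowing unscheduled visits at any time at the investigator's discretion. The subject has to come back anyway for fasting weight, a confirmatory endpoint, and at V10 to V32 for FPG. One return visit with one draw is a workable arrangement. The phrase in 8.1.1 could be read, with 8.2, as meaning only the fasting-dependent samples, and the laboratory manual, which is not shown, may say so.

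Much of this stands, and it limits the point. A reader might infer that 8.1.6 rules out a late sample altogether. It does not: the explicit out-of-window provision is tied to a sample that could not be analysed, so a sample never drawn is not clearly covered, but the general discretion remains. A reader might also infer that discontinued subjects are unlikely to return a second time. That is plausible, but the documents say nothing about it.

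The most tempting stronger reading is that D is biased in favour of IDegLira, because off-drug IDegLira subjects would be imputed as if on IGlar. Counting losses in that arm alone, 2 to 6 subjects with gaps of 0.3% to 1.0% would give a shift of up to about 0.03%. But IGlar discontinuers attend V32A under the same rule, and their lost values are imputed from largely the same model. The net shift depends on losses and gaps in both arms that the documents do not give, so no direction is shown.

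What the objection does not remove is the literal instruction in 8.1.1. A site can follow it exactly and still send a subject away without an HbA1c sample that could have been drawn.

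**Conclusion.** The point holds as a small data-completeness weakness in the wording of section 8.1.1, extended to V32A by Amendment 2. It is not a sample-size error and not a demonstrated bias. At V32A the plausible cost is about 1 to 12 measured week-26 values and 0.1 to 1.3 points of power. This rests on an assumed 2% to 20% unrecovered loss among at most about 62 subjects, fewer once withdrawals are taken out. The step 1 deletion adds to the cost in the IDegLira arm only, by discarding values that were already observed. It is worth correcting because the deferral gains nothing for HbA1c and the change costs almost nothing.

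**What to change.** In section 8.1.1, state that when a subject attends a fasting visit non-fasting, HbA1c and all other samples that do not require fasting are drawn at that visit, and that only FPG, lipids and body weight are re-scheduled within the visit window. Repeat this for V32A in section 8.1.7, where it means that HbA1c is drawn on the day and only body weight is re-scheduled. Align the laboratory manual with it.

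Cost: one sentence in each place and an occasional second venepuncture for subjects who return for FPG and lipids. At V32A no second draw is needed. Fasting weight and FPG keep their present protection, and N stays at 416.
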